### 9.1. Definitions of Adverse Events

An **Adverse Event** is an event that occurs during the course of a research protocol that either causes physical or psychological harm, or increases the risk of physical or psychological harm, or results in a loss of privacy and/or confidentiality to a research participant or others (such as family members).

Adverse events for MRI scans are very rare. Millions of MRI scans are performed in the US every year, and the FDA receives around 300 adverse event reports for MRI scanners and coils each year from manufacturers, distributors, user facilities, and patients. The majority of these reports describe heating and/or burns (thermal injuries). Second degree burns are the most commonly reported patient problem. Other reported problems include injuries from projectile events (objects being drawn toward the MRI scanner), crushed and pinched fingers from the patient table, patient falls, and hearing loss or a ringing in the ear (tinnitus). The FDA has also received reports concerning the inadequate display or quality of the MR images.

An **Anticipated Adverse Event** is one that is reasonably expected and/or listed in the protocol and consent form as a risk of participating in the research. Examples of an anticipated adverse event include, but are not limited to, the following:

- Discomfort during MRI scan which may stem from patient claustrophobia
- Injury from the strong magnetic field attracting projective magnetic objects

- Hearing harm from the loud knocking noises for the magnetic field and gradients
- Heating of the body from the radiofrequency energy during the MRI scan.
- The strong magnetic field may affect tattoos, metal implants or accessory medical devices, and/or can lead to burns or efficacy of device

An **Unanticipated Adverse Event** is one that was not reasonably expected and/or is not listed in the protocol and consent form as a risk of participating in the research.

A **Serious Adverse Event** is one whose magnitude or frequency is above expectation.

A **Related adverse event** is one that, in the opinion of the investigator, is likely caused by or affects the research.

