## 9.2. Reporting of Events by Clinical Sites

### 9.2.1. Relationship to the Study System

All adverse events will be reported to the IRB as soon as they occur, but no later than 5 working days of becoming aware of the event's occurrence.

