### 9.2.2. Degree of Severity

The degree of severity will be graded for the purposes of reporting as follows:

0-No AE (or within normal limits).

1-Mild; asymptomatic or mild symptoms; clinical or diagnostic observations only; intervention not indicated.

2-Moderate; minimal, local, or noninvasive intervention indicated; limiting age-appropriate instrumental activities of daily living (ADL).

3-Severe or medically significant but not immediately life-threatening; hospitalization or prolongation of hospitalization indicated; disabling; limiting self-care ADL.

4-Life-threatening consequences; urgent intervention indicated.

5-Death related to AE.

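### Section 9.1 defines a serious adverse event by expectation and not by outcome, so a burn or projectile injury leading to hospitalisation could be classed as not serious

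*Combined protocol and SAP*

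**What the plan says.** Section 9.1 (Definitions of Adverse Events) classifies events in two ways that bear on this point.

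- **Expectedness.** An anticipated event "is one that is reasonably expected and/or listed in the protocol and consent form as a risk of participating in the research". An unanticipated event is the complement. The examples of anticipated events include "Injury from the strong magnetic field attracting projective magnetic objects", and a further item on tattoos, implants and devices says that the field "can lead to burns or efficacy of device". Neither item has a severity limit.
- **Seriousness.** A serious adverse event "is one whose magnitude or frequency is above expectation". That is the whole definition.

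The nearest that 9.1 comes to an expected magnitude is background on reports to the FDA: "Second degree burns are the most commonly reported patient problem". It is not set as a threshold.

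Section 9.2.2 (Degree of Severity) has a separate scale from 0 to 5. Grade 3 reads in part "3-Severe or medically significant but not immediately life-threatening; hospitalization or prolongation of hospitalization indicated" and also covers disability. Grade 4 is a threat to life and grade 5 is death. No grade is linked to the term serious.

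Section 9.2.1 sets one reporting rule for everything: "All adverse events will be reported to the IRB as soon as they occur, but no later than 5 working days".

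Section 4.1 makes safety of the STAGE system the primary objective.

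**The concern.** Seriousness and expectedness answer different questions. Seriousness asks what happened to the subject; expectedness asks whether it was foreseen. Section 9.1 uses expectation for both, so the plan has no category that identifies events by their consequence.

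At stake is the meaning of any sentence in the study report about serious adverse events. A reader of a statement that none occurred will take it to mean no deaths, threats to life, admissions or disabling injuries. Under 9.1 it would mean only that nothing was judged to exceed an expectation that the plan never states. The error can run both ways: a consequential event left out, or a trivial one counted in. The study is meant to support a 510(k) submission (section 1.1) and enrols children from age 6 (section 6.1). The endpoints in 4.2 and the analyses in 8.3 concern image quality only, so the definitions and grades in section 9 are the main basis for anything said about safety.

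**Working it through.** The point concerns a definition, and the plan gives no figure to reproduce. The check is to apply 9.1 and 9.2.2 to the same events.

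**Step 1: what the rule needs.** To apply the 9.1 definition, a site needs an expected magnitude or an expected frequency for the event type. Neither 9.1 nor any other section sets one for burns or projectile injury.

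**Step 2: apply the rule.**

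| Event | Expectedness (9.1) | Grade (9.2.2) | Serious under 9.1? | Serious by outcome? |
|---|---|---|---|---|
| Burn leading to hospitalisation | Anticipated | 3 | Undetermined: no, if judged within expectation on both magnitude and frequency; yes, if either is judged exceeded | Yes |
| Projectile injury leading to hospitalisation | Anticipated | 3 | Undetermined, as above | Yes |
| Mild discomfort, more often than expected | Anticipated | 1 | Yes, on frequency | No |

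The first two rows can be missed and the third can be included.

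**Step 3: can the background figures settle it?** Two places hint at a rate.

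- Section 3.1 labels its paragraph on MRI risks as rare, which it defines as an incidence below 1%. That paragraph covers discomfort and nerve stimulation but does not name burns or projectile injury. Taken as the expectation for discomfort, one event in the minimum of 80 cases is 1/80 = 1.25%, above 1%. One event in the maximum enrolment of 120 is 1/120 = 0.83%, below 1%. The same mild event would change class with the denominator.
- Section 9.1 cites about 300 reports a year to the FDA against millions of scans. Assuming only one million scans, 300/1,000,000 = 0.03%; more scans give a lower figure. Any single event in this study, at 0.83% or more, would exceed that. These are counts of submitted reports across all problem types, and the plan does not adopt them as an expected rate.

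The two hints lead to different classifications, and neither is designated as the reference.

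**Step 4: is it repaired elsewhere?** The term serious adverse event is not used again after its definition. Section 9.2.2 names the relevant outcomes but does not connect them to it. Nothing repairs the definition.

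**The case against.** The strongest opposing case has four parts.

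- **The text does not force the bad result.** A reader might infer that any event on the anticipated list is automatically not serious. The documents do not support that. Listing settles that the type of event is foreseen, not its size or rate, and the definition is met if either magnitude or frequency is exceeded. Since 9.1 describes MRI adverse events as very uncommon, a single burn leading to hospitalisation could readily be judged above expectation. This objection stands: the classification is undetermined, and the supportable wording is that such an event could be classed as not serious.
- **Nothing goes unreported.** All adverse events go to the IRB on one 5-working-day clock whether serious or not, and a hospitalised injury is grade 3 whatever its label. This also stands, and it limits the harm to classification.
- **The label drives nothing in the plan.** It sets no reporting clock, endpoint, success rule or analysis, and no table of serious events is specified. That is correct as far as it goes. But safety is the primary objective, so the sponsor can be expected to say something about serious events, and 9.1 is the only definition available for it.
- **Risk is low.** The study is observational, with imaging without contrast administration and normally one visit. This bears on how often the defect would matter. It does not make the definition right.

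**Conclusion.** The concern holds in a limited form. The definition in 9.1 is a wrong stated rule and not merely a missing detail: it uses expectation in place of outcome, and because no expectation is quantified it cannot be applied consistently. A listed burn or projectile injury leading to hospitalisation could be left out of the serious category, and an excess of mild discomfort could be put in.

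No numerical size attaches to this. The effect is misclassification in any statement about serious events made under the primary safety objective. It is not non-reporting, and it does not touch the image-quality endpoints or the sample size. The conclusion assumes that the sponsor will make some statement about serious events, which the plan does not itself specify, and that no separate document available to sites supplies an outcome-based definition.

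**What to change.** - **Definition.** In 9.1, replace the definition with one based on the outcomes that 9.2.2 already names: death, life-threatening consequences, hospitalisation or its prolongation, and disability.
- **Separate attributes.** Record expectedness (anticipated or unanticipated) and severity grade alongside seriousness, each in its own field. Do not simply equate serious with grades 3 to 5. Grade 3 can also be reached through medical significance or loss of self-care without any of those outcomes, so that shortcut would replace one conflation with another.
- **Reporting.** State in 8.3 or 9 that serious events will be summarised on this basis.

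The cost is one definition, one line on reporting and, if not already present, a seriousness field on the adverse event form. Events already recorded can be reclassified where the record shows the outcome; the grade alone will not always show it for grade 3. The downside is that some anticipated events will now count as serious.

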## 9.2. Reporting of Events by Clinical Sites

### 9.2.1. Relationship to the Study System

All adverse events will be reported to the IRB as soon as they occur, but no later than 5 working days of becoming aware of the event's occurrence.

### 9.2.2. Degree of Severity

The degree of severity will be graded for the purposes of reporting as follows:

0-No AE (or within normal limits).

1-Mild; asymptomatic or mild symptoms; clinical or diagnostic observations only; intervention not indicated.

2-Moderate; minimal, local, or noninvasive intervention indicated; limiting age-appropriate instrumental activities of daily living (ADL).

3-Severe or medically significant but not immediately life-threatening; hospitalization or prolongation of hospitalization indicated; disabling; limiting self-care ADL.

4-Life-threatening consequences; urgent intervention indicated.

5-Death related to AE.

## 9.3. Device Failure and Malfunctions

Any device failure or malfunctions will be reported to the committee no later than 5 working days since the occurrence. FDA team will review the cause of the malfunction and if any sources are linked to 3rd party systems or software, they will be notified of the failure or malfunction.

## 10. TEAMS

### 10.1 Study Administrator

The Study Administrator is responsible for review of data from ongoing studies. Administrative personnel, under appropriate supervision, may be delegated tasks such as setting up files and labeling and filing of documents.

### 10.2 Study Monitor

The Study Monitor is a qualified individual responsible to oversee the progress of a clinical study and to act as liaison between the Sponsor and the Investigator/Site. A Study Monitor assigned to a study site is responsible for maintaining the Investigator study file for that site.

### 10.3 Study Sponsor (SpinTech, Inc.)

The Study Sponsor is required to demonstrate that the studies are conducted according to the generally accepted principles of Good Clinical Practice.

The Sponsor, or other owners of the data, should retain all of the Sponsor-specific essential documents pertaining to the trial. The Sponsor should retain all Sponsor-specific essential documents in conformance with the applicable regulatory requirement(s) of the country(ies) where the product is approved, and/or where the Sponsor intends to apply for approval(s).

If the Sponsor discontinues the clinical development of an investigational product (i.e. for any or all indications, routes of administration, or dosage forms), the Sponsor should maintain all Sponsor-specific essential documents for at least 2 years after formal discontinuation or in conformance with the applicable regulatory requirement(s).

The Sponsor specific essential documents should be retained until at least 2 years after the last approval of a marketing application in an ICH region and until there are no pending or contemplated marketing applications in and ICH region or at least 2 years have elapsed since the formal discontinuation of clinical development of the investigational product. These documents should be retained for a longer period however if required by the applicable regulatory requirement(s) or if needed by the Sponsor.

### 10.4 Qualification team

Per the SOP, the Qualification Team consists of members from the Clinical Affairs Department and other **SpinTech, Inc.'s** departments, as appropriate. The team is responsible for identifying, qualifying, and selecting Investigators.

The team will review the CV of the Investigators and assess the Investigator's qualifications, credentials, and experience in the intended therapeutic area. The team is also responsible to verify that medical licenses for all Investigators are current.

The team should also check the names of prospective Investigators against the FDA list of "Investigators Ineligible to Receive Investigational Products" (the "Blacklist") and the FDA/ORA Bioresearch Monitoring Information Page in order to research past issues with both the Investigator and site.

### 10.5 Principal Investigator and Co-Investigators

The Investigator should be able to demonstrate (e.g., based on retrospective data) a potential for recruiting the required number of suitable subjects within the agreed recruitment period. The investigator should have sufficient time to properly conduct and complete the trial within the agreed trial period, and should have available an adequate number of qualified staff and adequate facilities for the foreseen duration of the trial to conduct the trial properly and safely.

The investigator should ensure that all persons assisting with the trial are adequately informed about and trained on the approved protocol, the investigational product(s), and their trial-related duties and functions. A qualified physician, who is an Investigator for the trial, shall be responsible for all trial-related medical decisions. During and following a subject's participation in a trial, the Investigator should ensure that adequate

medical care is provided to a subject for any adverse events, including clinically significant laboratory values, related to the trial. The Investigator should inform a subject when medical care is needed for intercurrent illness(es) of which the Investigator becomes aware.

It is recommended that the Investigator inform the subject's primary physician about the subject's participation in the trial if the subject has a primary physician and if the subject agrees to the primary physician being informed. Although a subject is not obliged to give his/her reasons(s) for withdrawing prematurely from a trial, the investigator should make a reasonable effort to ascertain the reason(s), while fully respecting the subject's rights.

## 11. ADMINISTRATIVE RESPONSIBILITIES

### 11.1. Ethics Committee / Institutional Review Board Approval

An IRB/Ethics Committee reviews the appropriateness of the clinical trial protocol as well as the risks and benefits to study participants. It ensures that clinical trial participants are exposed to minimal risks in relation to any benefits that might result from the research.

IRB/Ethics Committee will review all study related materials before and during the trial.

The Ethics Committee should be collectively qualified to review the scientific, medical, and ethical aspects of the trial. An IRB/Ethics Committee should be composed of the following:

- at least 5 members
- members with varying backgrounds
- at least one member must represent a non-scientific area
- at least one member not affiliated with the institute or the trial site (independent member)
- competent members who are able to review and evaluate the science, medical aspect, and ethics of the proposed trial

### 11.2. Informed Consent

Informed consent is an ongoing process that must occur before any clinical trial-related procedures are conducted. The process consists of a document and a series of conversations between the clinical trial participant and the PI or study coordinator and delegated health care professionals, as appropriate.

The PI or study coordinator discusses the trial's risks, benefits and other aspects with the potential participant and, if required, the participant's legal representative, before the trial begins.

The PI or study coordinator gives the potential participant ample time and opportunity to ask questions about the trial and discuss it with relatives and family members.

If the potential participant decides to get involved in the trial, he or she provides voluntary consent by signing and dating the written informed consent document of which he or she also receives a copy. The participant has the right to withdraw consent at any time without penalty, repercussions or reason.

While the PI or study coordinator may delegate the task of administering and obtaining informed consent to a qualified individual, he or she is ultimately responsible for ensuring the process is conducted properly.

Informed Consent Guidelines

Investigators must follow the International Council on Harmonization (ICH) good clinical practice (GCP) guidelines. Section 1.28 describes the informed consent process, while the requirements and process for obtaining informed consent from a clinical trial participant are explained in section 4.8.

In addition to following ICH guidelines, investigators need to adhere to national and local regulatory requirements, sponsor requirements and privacy and personal data security regulations applicable in the country in which the study is being conducted.

The informed consent document must be fully approved by an institutional review board (IRB) or an independent ethics committee (IEC) prior to its use with trial participants.

#### Elements of Informed Consent Document

The informed consent form, which is a legal document, must include 20 ICH-required elements (section 4.8.10 of the GCP guidance). They include the purpose, duration, risks, benefits, costs and additional expenses of the trial; a description of the trial procedures; alternative care options; and volunteers' rights.

The document also must have at least two signature and date lines: one for the participant and another for the health care professional conducting the informed consent discussions with the participant.

Both the written document and the verbal consenting process must be presented in language the participant understands. It also needs to be documented appropriately.

#### Revisions to Informed Consent

Informed consent documents must be revised every time new safety information becomes available or there is a change in trial procedures, participant compensation or personnel noted on the consent form. Revisions to the informed consent document must be approved by an IRB/IEC prior to its use, and the informed consent process with the new information and documentation needs to be repeated with every clinical trial participant. The participant is then required to sign the revised form.

Consent: Written informed content will be obtained from the participant to ensure the subject understands the nature of the study, has adequate time to evaluate whether to participate in the study, also does not feel coerced in any way to undertake participation in the study. Subjects from vulnerable groups will not be included: non-English speakers, persons with diminished capacity, cognitive impairment, or mental illness, non-consenting participants (in emergency situations), pregnant women, fetus or neonates, terminally ill subjects, prisoners, or economically or educationally disadvantaged persons.

The participant will be informed that participation is voluntary and that he or she can withdraw from the study at any time.

### 11.3. Patient Recruitment

Patient recruitment will take place using the University's, Hospital's, or Imaging Center's protocols. Contact: Participants will be recruited by a notice/flyer at the clinical site as well as by person to person interaction/word of mouth. They will not have any cost or monetary incentive to be involved in the study. All participants must sign an informed consent to be involved in the study. The study requires one visit by the participant which will require 2 hours of their time. The participant will be explained the study and then given time to review and sign the informed consent as well as ask any questions they may have before signing. Review and signing of informed consent, participant intake including MRI survey including assessment that participant meets all inclusion/exclusion criteria, and imaging will take place in that time. No level of deception is made towards the participants and their scan data will not be made available to them under normal conditions. It will be conveyed to the participants that the study is to validate a new MRI method which decreases the scan time and that their images will be evaluated by a trained neuroradiologist

for the contrast and quality of the images. The informed consent will be presented by a research assistant, PI, or research nurse. Controls will be recruited from the local hospital/imaging center by word of mouth or the placement of flyers across campus. Additional recruitment will take place from lists in which subjects who have voluntarily showed interest through the university/hospital's research portal.

#### 11.4. Confidentiality

The confidentiality of records that could identify subjects should be protected, respecting the privacy and confidentiality rules in accordance with the applicable regulatory requirement(s).

#### 11.5. Amending the Protocol

A sponsor of an IND application is expected to submit a protocol amendment in cases when there are changes in the existing protocol that significantly affect safety of subjects, scope of the investigation, or scientific quality of the study. Such amendment should contain a brief description of the change and reference (date and number) to the submission that contained the original protocol.

For example, changes requiring an amendment to an IND application may include:

Any significant change in the design of a protocol (such as the addition or elimination of a control group).

Addition of a new test or procedure intended to improve monitoring for, or reduce the risk of, a side effect or adverse event; or elimination of a test intended to monitor safety.

Note: a protocol change intended to eliminate an apparent immediate hazard to human subjects may be implemented immediately, provided that FDA is subsequently notified by protocol amendment and the reviewing IRB is also notified.

